### EXPERIMENT 3: Optimal Intersession Interval

This experiment builds on previous understanding of the optimal intersession interval for spaced TBS which suggests that for cTBS, the optimal ISI is 15 minutes while with iTBS the optimal ISI is 30 minutes. We will utilize the burst frequency determined to be optimal from experiment 1. We will apply TBS over the left, dominant M1. TBS will be repeated two times separated by 15, 30, 45, or 60 min intersession interval. Subjects will attend eight sessions no <4 days apart, receiving the cTBSXX-15-cTBSXX, cTBSXX-30-cTBSXX, cTBSXX-45-cTBSXX, cTBSXX-60- cTBSXX, iTBSXX-15-iTBSXX, iTBSXX-30-iTBSXX, iTBSXX-45-iTBSXX, and iTBSXX-60-iTBSXX applied at 80 of RMT. The order in which they will receive each paradigm will be randomized between subjects. MEP recruitment curves and cortical silent period thresholds will be recorded at baseline, and at 0, 20, 40, 60, 90, and 120 min following the second TBS application.

Each subject will have 8 visits. 22 number of participants.

1. MEP----iTBSXX----15 min----iTBSXX----MEP
2. MEP----iTBSXX----30 min ----iTBSXX----MEP
3. MEP----iTBSXX----45 min ----iTBSXX----MEP
4. MEP----iTBSXX----60 min ----iTBSXX----MEP
5. MEP----cTBSXX----15 min ----cTBSXX----MEP
6. MEP----cTBSXX----30 min ----cTBSXX----MEP
7. MEP----cTBSXX----45 min ----cTBSXX----MEP
8. MEP----cTBSXX----60 min ----cTBSXX----MEP

XX=optimal burst frequency from experiment

Motor Evoked Potentials (MEPs)

Subjects will be seated in a comfortable chair for all procedures. Single-pulse TMS will be used to evoke MEPs from the right first dorsal interosseous (FDI) muscle.

Electromyographic recordings will be made from the right FDI using two Ag- AgCl surface electrodes arranged in a belly-tendon montage. Signals will be sampled at a rate of 5 kHz, amplified #1000 and filtered 20–1000 Hz before we store on a computer for offline analysis. Single-pulse TMS with monophasic waveform will be applied using a Magventure Magpro X100 magnetic stimulator Magventure, Farum, Denmark connected to a figure-of-eight magnetic coil external wing diameter, 90 mm. The coil will be held tangentially to the skull over the left M1, with the handle pointing 45° posterolaterally. The optimal scalp site for evoking MEPs in the right FDI will be identified and marked using a Watersoluble felt marker, and the intensity of stimulation will be adjusted to evoke baseline MEPs of approximately 1 mV amplitude measured peak-to peak.

### TBS Paradigms

iTBS and cTBS will be applied with biphasic waveform using a Magventure Magpro Magventure, Farum, Denmark. One of two cTBS and two iTBS paradigms with varying pulse configurations will be employed in this study. cTBS50 consists of a total of 600 stimuli applied in bursts of 3 stimuli at 20 ms intervals 50 Hz, with bursts repeated at 200ms intervals 5Hz.

In the cTBS30 paradigm, bursts consisted of 3 stimuli applied at intervals of 33.3 ms 30 Hz, with bursts repeated at 167 ms intervals 6 Hz.

As with the cTBS50 paradigm, cTBS30 consists of a total of 600 stimuli. iTBS50, consists of a total of 600 stimuli applied in bursts of 3 stimuli at 20 ms intervals 50 Hz, with bursts repeated at 200ms intervals 5Hz and an 8 second intertrain interval between triplets. iTBS30 consists of bursts consisted of 3 stimuli applied at intervals of 33.3 ms 30 Hz, with bursts repeated at 167 ms intervals 6 Hz for three bursts then an 8 second intertrain interval.

In Experiment 1, the optimal burst frequency for both cTBS and iTBS will be determined and that optimal cTBS and iTBS frequency will be utilized in this portion of the study.

#### EXPERIMENT 4: Neuroimaging

This experiment will form the bulk of the study and involves determining the rs fc MRI changes seen with spaced TBS, as well as determining how these rs fc MRI changes correlate with iTBS/cTBS response. Functional connectivity between pre-motor and motor cortex will be assessed. MRIs will be done at the Center for Cognitive and Neurobiological Imaging at Stanford University, or at the Richard Lucas Center for Imaging. All scans will be governed by each respective imaging center's safety protocols.

Resting state functional MRI and MR spectroscopy may be performed. The experimental procedures TBS applications of the fMRI sessions will be timed equivalent to the time 0 post spaced theta-burst stimulation of the MEP sessions from Experiment 2. In addition to the MEP acquisition, resting-state fMRI time series will be acquired at baseline and after the second application of cTBS and iTBS. Before the baseline fMRI measurements, the "hotspot" and RMT will be assessed using the neuronavigation setup. Subjects will attend two sessions no <4 days apart, receiving the cTBSXXYY-cTBSXX, and iTBSXX-YY-iTBSXX applied at 80 of RMT. The order in which they will receive each paradigm will be randomized between subjects. The fMRI sessions will start with a baseline resting-state scan duration 10 min where subjects will be instructed to lie motionless in the scanner with open eyes fixating a red cross, which was presented on a screen visible through a mirror attached to the MR head coil. After completion of the resting-state MRI, subjects will be asked to perform an active motor task, which will serve as a functional localizer for determining coordinates of M1 and other motor related regions for subsequent analyses.

This "activity" condition will be acquired after the resting state scan. After completion of the baseline fMRI session, subjects will be transported from the scanner to the anteroom of the MR console again sitting in the MR wheelchair without moving their right arm.

After coregistration with the neuronavigation system, spaced TBS will be applied separated by YY min controlled by a stopwatch. After the TBS, there will be another resting-state fMRI. The time protocol in the fMRI sessions will be identical to the one used in the MEP sessions.

Each subject will have 2 visits.

1. MRI----iTBSXX---YY min----iTBSXX---MRI
2. MRI----cTBSXX---YY min ----cTBSXX---MRI

XX=optimal burst frequency from experiment 1  
YY=optimal intersession interval from experiment 2

#### Motor Evoked Potentials (MEPs)

Subjects will be seated in a comfortable chair for all procedures. Single-pulse TMS will be used to evoke MEPs from the right first dorsal interosseous (FDI) muscle.

Electromyographic recordings will be made from the right FDI using two Ag–AgCl surface electrodes arranged in a belly-tendon montage. Signals will be sampled at a rate of 5 kHz, amplified ##1000 and filtered 20–1000 Hz before we store on a computer for offline analysis.

Single-pulse TMS with monophasic waveform will be applied using a Magventure Magpro X100 magnetic stimulator Magventure, Farum, Denmark connected to a figure-of-eight magnetic coil external wing diameter, 90 mm. The coil will be held tangentially to the skull over the left M1, with the handle pointing 45° posterolaterally. The optimal scalp site for evoking MEPs in the right FDI will be identified and marked using a watersoluble felt marker, and the intensity of stimulation will be adjusted to evoke baseline MEPs of approximately 1 mV amplitude measured peak-to peak.

#### TBS Paradigms

iTBS and cTBS will be applied with biphasic waveform using a Magventure Magpro Magventure, Farum, Denmark. One of two cTBS and two iTBS paradigms with varying pulse configurations will be employed in this study. cTBS50 consists of a total of 600 stimuli applied in bursts of 3 stimuli at 20 ms intervals 50 Hz, with bursts repeated at 200ms intervals 5Hz.

In the cTBS30 paradigm, bursts consisted of 3 stimuli applied at intervals of 33.3 ms 30 Hz, with bursts repeated at 167 ms intervals 6 Hz. As with the cTBS50 paradigm, cTBS30 consists of a total of 600 stimuli. iTBS50, consists of a total of 600 stimuli applied in bursts of 3 stimuli at 20 ms intervals 50 Hz, with bursts repeated at 200ms intervals 5Hz and an 8 second intertrain interval between triplets. iTBS30 consists of bursts consisted of 3 stimuli applied at intervals of 33.3 ms 30 Hz, with bursts repeated at 167 ms intervals 6 Hz for three bursts then an 8 second intertrain interval. In Experiment 1, the optimal burst frequency for both cTBS and iTBS will be determined and that optimal cTBS and iTBS frequency will be utilized in this portion of the study.

#### EXPERIMENT 5: AFFECTIVE STATE

This experiment will investigate the effect of TMS-induced neuroplasticity on evoked-related potential (ERP) responses to emotional and neutral faces, and motor-evoked

potential MEP responses to motor cortex 1 stimulation, as measured by electroencephalogram EEG and electromyogram EMG, respectively. ERP and MEP measurements will be taken prior to and following the theta burst TMS.

#### Evoked Related Potentials (ERPs)

Subjects will be seated in a comfortable chair for all procedures. EEG recordings will be made while subjects view emotional and neutral faces displayed on a computer screen. Subjects will then undergo the iTBS or cTBS protocol (see below). ERP and MEP responses will be measured again following TBS and compared to pre-TBS ERPs to measure the amount and valence of plasticity induced by TBS, and how this was modulated by the induced affective state.

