## b. Objectives

Please note TMS/TBS are used interchangeably in this protocol as they refer to different settings on the same device, a transcranial magnetic stimulation device, and both types of settings will be used for this study.

This study proposes to: 1 - determine the heart rate changes that are seen with TMS stimulation. 2- determine the optimal burst frequency for TMS, 3-determine the optimal intersession interval for TMS, 4- compare the results of #1 and #2 in the same subjects, 5- determine the effect of TMS/TBS on the resting state functional connectivity. 6- in healthy participants, assess the regulation of neuroplasticity by affective state.

Aim 1: To determine the heart rate changes seen with TMS/TBS.

Hypothesis 1: Heart rate changes will be observed following stimulation.

Aim 2: To determine the optimal burst frequency.

Hypothesis 2: For cTBS, the optimal frequency will be 30Hz bursts at 6Hz while iTBS will be the traditional 50Hz bursts at 5Hz.

Aim 3: To determine the optimal intersession interval for spaced TBS.

Hypothesis 3: For cTBS, the optimal ISI will be 15 min while with iTBS the optimal ISI will be 30 min.

Aim 4: To determine the effect of spaced TBS on the resting state functional connectivity.

Hypothesis 4: Optimized spaced iTBS and cTBS will produce changes in the resting state functional connectivity between pre-motor and motor cortex. Those who have less fc change from iTBS will experience maximal cTBS change in fc (correlated with change in MEP) and vice versa.

Aim 5: To determine the effect of TMS/TBS on the resting state functional connectivity.

Aim 6: To assess the regulation of neuroplasticity by affective state in healthy control participants.

Hypothesis 6: Changes in amplitude and frequency band power of ERP responses to emotional faces following iTBS and cTBS will be differentially affected by different induced affective states. Changes in MEP amplitude following iTBS and cTBS will be differentially affected by different induced affective states.

This study has broad implications ranging from advancing our understanding of the basic mechanisms of TBS on brain function, cerebral blood flow, and pain perception and therapeutic implications that could impact classical rTMS treatment schedules based on the duration of effects of spaced TBS.

---

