#### EXPERIMENT 1: Heart rate changes

The first experiment will determine what heart rate changes are seen following TMS/TBS stimulation. Please note some participants will only be included in experiment 1, availability and scheduling permitting. Subjects will attend 2 sessions where they will receive TMS/iTBS at 70 -100 of active or resting MT, as determined by the investigator. They will receive either active or sham during a session, and the sessions will be in a randomly assigned order.

Stimulation may be applied to the vertex, Beam F3 location, or location determined by neuronavigation. These are all standard locations for stimulation. Various heart rate measurements and cortisol and/or other lab tests will be collected before and after stimulation. fMRI will be completed before and after stimulation. Various questionnaires (e.g. regarding mood will be collected before/after stimulation). Tasks designed to induce mild mental stress (e.g. mental math or similar) will be used during the experiment to create equivalent baseline conditions for all subjects.

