#### TBS Paradigms

iTBS and cTBS will be applied with biphasic waveform using a Magventure Magpro Magventure, Farum, Denmark. Two cTBS and two iTBS paradigms with varying pulse configurations will be employed in this study. cTBS50 consists of a total of 600 stimuli applied in bursts of 3 stimuli at 20 ms intervals 50 Hz, with bursts repeated at 200ms intervals 5Hz. In the cTBS30 paradigm, bursts consisted of 3 stimuli applied at intervals of 33.3 ms 30 Hz, with bursts repeated at 167 ms intervals 6 Hz. As with the cTBS50 paradigm, cTBS30 will consist of a total of 600 stimuli. iTBS50, consists of a total of 600 stimuli applied in bursts of 3 stimuli at 20 ms intervals 50 Hz, with bursts repeated at 200ms intervals 5Hz and an 8 second intertrain interval between triplet. iTBS30 consists of bursts consisted of 3 stimuli applied at intervals of 33.3 ms 30 Hz, with bursts repeated at 167 ms intervals 6 Hz for three bursts then a 8 second intertrain interval. As with the iTBS50 paradigm, iTBS30 will consist of a total of 600 stimuli. The intensity of TBS

application will be set relative to resting motor threshold (RMT), measured using a biphasic pulse waveform with the rTMS coil. RMT will be defined as the minimum stimulus intensity sufficient to evoke MEPs in the right FDI at rest with peak-to-peak amplitudes of at least 50  $\mu$ V in five of 10 consecutive trials. After TBS, MEP recruitment curves and cortical silent period thresholds will be recorded at 0, 20, 40, 60, 90, and 120 min following TBS applications.

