#### TBS Paradigms

iTBS and cTBS will be applied with biphasic waveform using a Magventure Magpro Magventure, Farum, Denmark. One of two cTBS and two iTBS paradigms with varying pulse configurations will be employed in this study. cTBS50 consists of a total of 600 stimuli applied in bursts of 3 stimuli at 20 ms intervals 50 Hz, with bursts repeated at 200ms intervals 5Hz. In the cTBS30 paradigm, bursts consisted of 3 stimuli applied at intervals of 33.3 ms 30 Hz, with bursts repeated at 167 ms intervals 6 Hz.

As with the cTBS50 paradigm, cTBS30 consists of a total of 600 stimuli. iTBS50, consists of a total of 600 stimuli applied in bursts of 3 stimuli at 20 ms intervals 50 Hz, with bursts repeated at 200ms intervals 5Hz and an 8 second intertrain interval between triplets. iTBS30 consists of bursts consisted of 3 stimuli applied at intervals of 33.3 ms 30 Hz, with bursts repeated at 167 ms intervals 6 Hz for three bursts then an 8 second intertrain interval.

In Experiment 1, the optimal burst frequency for both cTBS and iTBS will be determined and that optimal cTBS and iTBS frequency will be utilized in this portion of the study. Subjects will view movie clips tailored to induce primary affective states during the iTBS or cTBS protocol targeted to either dlPFC or area M1.

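### In Experiment 5, pre-to-post change within one TBS type combines film and TBS effects, so it does not by itself measure TBS-induced plasticity or its modulation by affective state

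*Protocol*

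**What the plan says.** All places are in the protocol.

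- **Experiment 5, opening paragraph:** "ERP and MEP measurements will be taken prior to and following the theta burst TMS".
- **Experiment 5, Evoked Related Potentials (ERPs):** the post-TBS ERP and MEP responses are compared with the pre-TBS ERPs (no pre-TBS MEP is named as comparator) "to measure the amount and valence of plasticity induced by TBS, and how this was modulated by the induced affective state".
- **Experiment 5, TBS Paradigms:** "Subjects will view movie clips tailored to induce primary affective states during the iTBS or cTBS protocol targeted to either dlPFC or area M1".
- **Objectives, Hypothesis 6:** "Changes in MEP amplitude following iTBS and cTBS will be differentially affected by different induced affective states". A parallel sentence covers ERP amplitude and band power.
- **Experiment 1:** "They will receive either active or sham during a session, and the sessions will be in a randomly assigned order". This is the only place where sham appears.
- **Experiment 4:** "The order in which they will receive each paradigm will be randomized between subjects". Experiments 2 and 3 say the same. Experiment 5 has no such statement.

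Experiment 5 gives no number of films, film length, sample size or post-TBS measurement time. Experiments 2 and 3 list MEP times from 0 to 120 min.

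**The concern.** Two things happen between the pre and post measurements: the participant watches a mood film and receives active stimulation. The protocol attributes the whole change to stimulation. One of the outcomes is the ERP to emotional faces, which a mood film could plausibly shift directly. With no stated post-TBS measurement time, carry-over from the film is not ruled out.

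Aim 6 is at stake. If iTBS under one film gives a different change from iTBS under another, the text invites the conclusion that affective state regulated plasticity. The same result would arise if TBS did nothing and the two films simply moved the outcome by different amounts.

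**Working it through.** The protocol gives no figure for Experiment 5 to reproduce. The check is which contrasts the described conditions can identify.

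**1. Model.** For affective state a and TBS type t (i or c), write the mean pre-to-post change as D(a,t) = F(a) + T(a,t). F(a) is the change with the film alone, including time and repetition. T(a,t) is the further change due to TBS under that state.

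**2. Within one TBS type.** For states A and B under iTBS:

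D(A,i) − D(B,i) = [F(A) − F(B)] + [T(A,i) − T(B,i)].

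The second bracket is modulation of TBS plasticity and the first is a pure film difference. Only their sum is observed. Likewise D(A,i) alone gives F(A) + T(A,i), not the amount or direction of plasticity.

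**3. Interaction.** [D(A,i) − D(B,i)] − [D(A,c) − D(B,c)] = [T(A,i) − T(B,i)] − [T(A,c) − T(B,c)].

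The film terms cancel if F is the same under both types and every state is run with both types. If F depends on type, its own state-by-type difference stays in the contrast.

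**4. Rank check.** The number of states is not stated, so 2 and 3 were assumed, with states fully crossed with both TBS types.

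| Conditions | States | Cells | Parameters | Rank |
|---|---|---|---|---|
| Active iTBS and cTBS, each with film | 2 | 4 | 6 | 4 |
| Active iTBS and cTBS, each with film | 3 | 6 | 9 | 6 |
| As above plus sham with film | 2 | 6 | 6 | 6 |
| As above plus sham with film | 3 | 9 | 9 | 9 |

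In the first two rows the film difference, the TBS effect and its modulation within one type are not estimable; the interaction in step 3 is. With film-matched sham, all are estimable.

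**5. Side note on stimulation length.** By Experiment 5, TBS Paradigms, cTBS has 600 stimuli in bursts of 3, so 600/3 = 200 bursts. At 200 ms this is 200 × 0.200 = 40.0 s; at 167 ms it is 200 × 0.167 = 33.4 s. iTBS adds 8 s gaps and lasts longer. If clips run only during stimulation, film exposure differs by type and an equal F should not be assumed.

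**6. Precision.** Assume each participant contributes every cell, change scores have SD 1 and correlation r between sessions, and n is the number of participants. The simple contrast has SE = √(2(1−r)/n); the interaction has SE = √(4(1−r)/n).

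- n = 30 (the full MRI+rTMS group), r = 0: √(2/30) = 0.258 and √(4/30) = 0.365.
- n = 30, r = 0.5: √(1/30) = 0.183 and √(2/30) = 0.258.
- n = 20, r = 0: √(2/20) = 0.316 and √(4/20) = 0.447.

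The interaction's standard error is √2 = 1.41 times larger in each case.

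**The case against.** The best defence is that Hypothesis 6 speaks of changes after both iTBS and cTBS being differentially affected, which can be read as the interaction in step 3. On that reading an equal film effect drops out. This stands in part. A reader might infer that film and TBS effects cannot be separated anywhere in Experiment 5, and that goes too far. But the defence needs every film paired with both TBS types, which is not stated, and it does not rescue the sentence under Evoked Related Potentials, which claims the amount and direction of plasticity itself.

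A reader might also infer a 14- to 17-fold imbalance in film exposure. Experiment 5 describes iTBS30 as running "for three bursts then an 8 second intertrain interval", and Experiment 2 adds "As with the iTBS50 paradigm, iTBS30 will consist of a total of 600 stimuli". Together these give roughly 550 to 560 s against 33 to 40 s for cTBS. The documents do not support this as a finding. No clip length is given, so clips need not be confined to stimulation. Hypothesis 2 expects iTBS50, not iTBS30, to be optimal, and the iTBS50 text is unclear about what the 8 s gap separates. Also, 600 stimuli in nine-pulse trains gives 66.7 trains, not a whole number. Only the direction stands: cTBS is shorter.

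A last objection is that the choice of contrast belongs in the SAP, which is not shown. That is fair for the model. It is not fair for the conditions run and how films are paired and timed, because no later analysis can recover a condition that was never run.

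**Conclusion.** The point holds for comparisons within one TBS type. As written, that change combines film and TBS effects, and a between-state difference could come from the films alone. The protocol's statement that it measures TBS-induced plasticity and its modulation is not supported by the conditions described.

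The state by TBS type interaction is defensible if states and types are crossed and the film effect is equal under both. It cannot show modulation common to iTBS and cTBS.

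No rate of false conclusions can be given, since the film effect, number of films and sample size are all unstated. The identifiability result needs none of them; the precision figures rest on the assumptions in step 6. The consequence is confined to Aim 6. The stated primary endpoint, duration of TBS effect, is not touched.

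**What to change.** 1. **Evoked Related Potentials (ERPs).** State that post-TBS ERP and MEP are compared with pre-TBS ERP and MEP respectively, that the change combines film and TBS effects, and that between-film differences within a TBS type will not be reported as regulation of TBS-induced plasticity. Cost: wording only.

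2. **Hypothesis 6 and Experiment 5.** Rest any modulation claim on the affective state by TBS type interaction. Pair each film with both TBS types in randomised order, with the same film length and the same film-to-measurement interval for both. State the limits: it assumes an equal film effect under both types; film overlap with stimulation still differs because cTBS is shorter; it misses modulation common to both; and it is less precise than the simple contrast. Cost: one rule on pairing, order and timing. With two films (an assumption), this is 2 × 2 = 4 sessions per target, or 8 if both targets are studied in each participant, to be reconciled with the 4 days in Planned Duration of the Study.

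3. **Modulation common to both types.** State that no such claim will be made unless a film-matched sham is added. Sham is optional. With two films it would add 2 to 4 sessions per target, depending on whether it is matched to one or both TBS types.
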